7.7. Electrocardiography

Twelve-lead ECGs will be conducted before other assessments (eg, blood draws and administration of questionnaires) at the time points detailed in [Table 2](#). The ECGs should be performed after the patient has been supine for at least 5 minutes. The ECGs will be performed in triplicate, with approximately 1 to 5 minutes between recordings.

A qualified physician at a central diagnostic center will be responsible for interpreting the ECG. Electrocardiograms should be performed and transmitted according to the central ECG reading instructions provided in the ECG user manual. Electrocardiogram equipment will be provided to all clinical sites.

Although the ECG interpretation will be performed centrally, the clinical evaluation remains the investigator's responsibility.

The ECG will be evaluated by the investigator at the time of recording (signed and dated), and the printout should be kept in the source documentation file. When potentially clinically significant findings are detected by the investigator, a cardiologist should be consulted for a definitive interpretation. All communications and diagnoses should be filed in the source documentation file. The investigator's interpretation will be recorded in the CRF regardless of the central reading interpretation. Any abnormal findings assessed by the investigator as clinically significant should be recorded in the relevant CRF modules (eg, adverse event, medical history).

Objective alerts are predefined as described in the central ECG reading manual. In these cases, the site and the sponsor will be informed immediately.

Any unscheduled ECGs must also be submitted for central ECG reading.

All ECG results outside of the reference ranges will be judged by the investigator as belonging to one of the following categories:

- abnormal and not clinically significant
- abnormal and clinically significant

Any ECG finding that is judged by the investigator as a potentially clinically significant change (worsening) compared with a baseline value will be considered an adverse event, recorded on the source documentation and in the CRF, and monitored as described in Section 7.1.2.

7.8. Immunogenicity

Blood samples for serum ADA assessment will be collected at the time points detailed in [Table 2](#). Blood samples for ADA assessment will also be collected upon observation of any severe hypersensitivity reaction and anaphylaxis. Bioanalytical personnel should be made aware of anaphylaxis occurrence as soon as possible in case an anti-fremanezumab IgE assay is needed. Patients who are discontinued early for any reason or do not enroll in the double-blind, long-term safety study for treatment, for any reason, will be offered the option to enter the long-term safety study for the purpose of evaluating ADAs and safety (adverse events and concomitant medications) approximately 7.5 months after administration of the last dose of IMP.

Samples from placebo-treated patients will not be analyzed unless the patient elects to enroll into the extension study where the patient will receive fremanezumab treatment. In this case the pre-dose (baseline) sample from the rolled-over placebo patient will be analyzed along with post-treatment samples collected in the extension study and reported in the extension study.

7.9. Assessment of Suicidality

The study population being administered fremanezumab should be monitored appropriately and observed closely for suicidal ideation and behavior or any other unusual changes in behavior. Consideration should be given to discontinuing fremanezumab in participants who experience signs of suicidal ideation or behavior.

Families and caregivers of participants being treated with fremanezumab should be instructed to monitor participants for the emergence of unusual changes in behavior, as well as the emergence

of suicidal ideation and behavior, and to report such symptoms immediately to the study investigator.

The eC-SSRS will be used to assess the patient’s suicidal ideation (severity and intensity) and behavior (Posner et al 2011). The eC-SSRS Baseline/Screening version will be completed by the patient at visit 1, and the eC-SSRS Since Last Visit version will be completed by the patient at every visit thereafter, including unscheduled visits. Any positive findings on the eC-SSRS Since Last Visit version requires evaluation by a physician or doctoral-level psychologist.

A positive finding will be defined as a current suicide ideation with some intent to act and no plan. The investigator, based on his medical judgment, will determine if the patient should be seen by a mental health specialist and if he/she should continue participating in the study. If a patient reports current suicide ideation with specific plan and intent, then the patient should be immediately discontinued from the study and seen by a mental health specialist.

Any patient should be excluded if any suicidal behaviors are reported.

Any patient with lifetime behaviors (actual, interrupted, and aborted attempts and preparatory actions) should be excluded and/or discontinued from the study.

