4.3. Withdrawal Criteria and Procedures

Each patient is free to withdraw from the IMP and/or study at any time, without prejudice to their continued care. Patients must be withdrawn from the IMP and/or study if any of the following events occur:

1. Patient withdraws consent or requests discontinuation from the IMP and/or study for any reason.
2. Patient develops an illness that would interfere with his/her continued participation.
3. Patient is noncompliant with the study procedures and assessments or administration of IMPs in the opinion of the investigator.
4. Patient takes prohibited concomitant medications as defined.
5. A female patient has a confirmation of pregnancy during the study from a positive pregnancy test.
6. The sponsor requests withdrawal of the patient.
7. Patient experiences an adverse event or other medical condition which indicates to the investigator that continued participation is not in the best interest of the patient.
8. The investigator and/or sponsor may withdraw an individual patient from the study at any time for any reason (eg, lack of efficacy, protocol deviation as defined in Section 10, noncompliance, or adverse event). In addition, patients with positive eC-SSRS findings or abnormal hepatic laboratory values (eg, ALT, AST, ALP, GGT, bilirubin [total, direct, or indirect], or INR) may meet criteria for discontinuation from the IMP as summarized in [Appendix J](#).

In the event that a patient was incorrectly randomized and has already started taking the study drug, a risk/benefit evaluation should take place between the investigator and sponsor and a strong clinical justification must be provided if the patient is not withdrawn from study drug.

Patients should be treated with standard of care after withdrawal from or termination of the study as appropriate.

Investigators should attempt to obtain information on patients in the case of withdrawal or discontinuation. Results of any evaluations and observations, together with a narrative describing the reason(s) for withdrawal, must be recorded in the source documents. The case report form (CRF) must document the primary reason for withdrawal or discontinuation.

See [Appendix F](#) for information regarding how the study will define and address lost to follow-up patients to help limit the amount and impact of missing data.

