APPENDIX J. GUIDANCE ON SAFETY MONITORING

Guidance on Monitoring Patients with Elevated Liver Function Tests

Liver enzymes (ALT, AST, GGT, and ALP) as well as total, direct, and indirect bilirubin will be measured at each study visit.

In any case of elevated ALT or AST to a level exceeding $\geq 2 \times$ the ULN (including patients whose baseline ALT or AST levels are $\geq 2 \times$ and $\leq 3 \times$ the ULN, who may be enrolled in the study), a thorough medical history and physical examination with a focus on liver disease should be undertaken.² In addition, the patient should be instructed to refrain from alcoholic beverages.

In case of symptoms compatible with drug-induced liver injury during the study, patients will be instructed to return to the study center for an unscheduled visit or to go to the emergency room to measure liver enzymes as soon as possible. Solitary elevations of total, direct, or indirect bilirubin, not accompanied by elevations of ALT or AST should be managed according to the discretion of the treating physician.

Elevation of Either ALT or AST to $\geq 3 \times$ ULN

Confirmation is required prior to IMP discontinuation in cases of elevation of either ALT or AST $\geq 3 \times$ ULN. (Note: In cases of elevation of ALT or AST $\geq 8 \times$ the ULN, no confirmation is required prior to IMP discontinuation, but the assessments below should be performed.) The following procedures should be followed:

- The day in which the abnormal value is received from the laboratory will be considered as day 0.
- The investigator should repeat the test for confirmation purposes (this may be performed in a local laboratory along with complete blood cell [CBC] count and differential to assess for eosinophilia; in general, in case a blood sample is sent to a local laboratory, the following assessments [and reference ranges] are mandatory: ALT [serum glutamic pyruvic transaminase], AST [serum glutamic oxaloacetic transaminase], ALP, bilirubin [total, direct, and indirect], CBC [with differential for eosinophil count, separate tube], and INR [separate tube; not to be sent in a confirmatory test]). The investigator should also question the patient regarding symptoms.

The abnormality will be regarded as confirmed in each of the following scenarios:

- the baseline value was within the normal range and ALT or AST is still $\geq 3 \times$ the ULN
- the baseline value was above the ULN and ALT or AST is $\geq 2 \times$ the baseline value

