1.3. Safety Endpoints

The safety endpoints are as follows:

- occurrence of adverse events throughout the study
- clinical laboratory (serum chemistry, hematology, coagulation, and urinalysis) test results at each visit
- vital signs (systolic and diastolic blood pressure, oral temperature, and pulse rate) measurements at each visit. Note: Oxygen saturation will be measured in cases of suspected anaphylaxis and severe hypersensitivity. Respiratory rate will also be measured in these cases but not as a standard vital sign.

- 12-lead electrocardiogram (ECG) findings at screening, baseline, and week 12
- use of concomitant medication during the study
- clinically significant changes in physical examinations, including body weight
- injection site reaction (ie, erythema, induration, and ecchymosis) and injection site pain assessments
- occurrence of hypersensitivity/anaphylaxis reactions
- suicidal ideation and behavior as measured by the electronic Columbia Suicide Severity Rating Scale (eC-SSRS)

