8.6. Electronic Columbia Suicide Severity Rating Scale

The eC-SSRS Baseline/Screening version will be completed at visit 1, and the eC-SSRS Since Last Visit version will be completed at all other visits (visits 2, 3, 4, and 5), including unscheduled visits. Any positive findings on the eC-SSRS Since Last Visit version require evaluation by a physician or doctoral-level psychologist.

Data for patients with positive findings (having suicidal ideation or suicidal behavior) will be listed.

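### The protocol and SAP define a positive eC-SSRS finding differently, the protocol refers such findings to an appendix with no suicidality criteria, and the SAP plans only a listing for this safety endpoint

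*Protocol*

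**What the plan says.** Protocol 7.9 sets the trigger: "Any positive findings on the eC-SSRS Since Last Visit version requires evaluation by a physician or doctoral-level psychologist". It then defines the term: "A positive finding will be defined as a current suicide ideation with some intent to act and no plan". For such a finding the investigator judges whether a mental health specialist is needed and whether the patient stays in the study. More serious states are handled separately in 7.9: "If a patient reports current suicide ideation with specific plan and intent, then the patient should be immediately discontinued from the study", with referral to a specialist, and patients with suicidal behaviour are to be excluded or discontinued. The section opens with a general instruction to observe patients closely and to consider stopping fremanezumab if signs of ideation or behaviour appear.

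Protocol 4.3 adds that "patients with positive eC-SSRS findings or abnormal hepatic laboratory values" may meet criteria for stopping the investigational product, and says that Appendix J summarises those criteria. Section 3.4 says the same. Appendix J opens with "Guidance on Monitoring Patients with Elevated Liver Function Tests".

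SAP 8.6 restates the trigger: "Any positive findings on the eC-SSRS Since Last Visit version require evaluation by a physician or doctoral-level psychologist". Its only planned output is this: "Data for patients with positive findings (having suicidal ideation or suicidal behavior) will be listed". Protocol 2.1 and SAP 1.3 both name ideation and behaviour on the eC-SSRS as a safety endpoint. Protocol 9.7 commits to describing safety data in total and per arm, with counts and percentages for categorical variables.

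**The concern.** One term carries two meanings, and it is the term that triggers an evaluation. A patient who reports ideation without intent is positive in the SAP's sense and not in the protocol's. The reader who follows protocol 3.4 or 4.3 to learn what a positive finding means for continued dosing arrives at an appendix that does not address the question.

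The reporting is also thinner than the protocol's own rule. A declared safety endpoint would reach the study report as a list of patients, with no prespecified count, percentage or baseline reference per arm. The trial has no data monitoring committee (protocol 5.9.3), so the final report is the natural place for any imbalance between arms to be seen.

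**Working it through.** No arithmetic applies, because the plan gives no figure on this point. The check sets the current, unredacted texts side by side.

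**Step 1: the definition.** The division into four outcomes below is mine; it follows the distinctions made in protocol 7.9.

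| Outcome on the eC-SSRS | Positive in protocol 7.9? | Other rule in 7.9 | Positive in SAP 8.6? |
|---|---|---|---|
| Ideation without intent | No | General observation; consider stopping drug | Yes |
| Ideation with some intent, no plan | Yes | Same general rule | Yes |
| Ideation with plan and intent | Not within the definition | Discontinue; specialist referral | Yes |
| Suicidal behaviour | Not within the definition | Exclude and/or discontinue | Yes |

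The meanings agree on one row of four. In the last two rows the protocol acts through other sentences. That leaves the first row as the main practical gap: such a patient is positive in the SAP, but nothing in 7.9 clearly calls for the formal evaluation.

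**Step 2: the cross-reference.** Protocol 3.4 and 4.3 pair eC-SSRS findings with abnormal hepatic values and send both to Appendix J. The appendix covers confirmation of raised transaminases, further tests, monitoring by degree of elevation, stopping rules and follow-up. Every stopping rule concerns liver enzymes or their monitoring. The reference works for the hepatic half and fails for the eC-SSRS half. The suicidality rules that do exist are in 7.9, which neither section cites at that point.

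**Step 3: the output.** Four statements bear on this:

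- Protocol 9.7: safety data described in total and per arm, with counts and percentages.
- SAP 8.1: safety summaries by treatment group are the default, unless stated otherwise. It names no eC-SSRS variable, category or table.
- SAP 8.6: a listing only.
- SAP 8.5, the section just before: both summaries and a listing for suspected anaphylaxis.

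Where the SAP intends a summary of a specific safety assessment, it says so. SAP 16 declares no change from the protocol's analyses, so the difference from protocol 9.7 is not acknowledged.

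**Step 4: baseline.** Exclusion criterion g in protocol 4.2 bars past attempts and current active ideation. Other ideation may be present at entry. SAP 8.6 does not separate findings recorded before the first dose from those recorded after it.

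**The case against.** The strongest reply is that patients are managed under the protocol alone. Every site works from 7.9. The SAP's introduction sends readers to the protocol for conduct and operational matters, and the wider wording appears only in the sentence about what is listed. The clause giving the SAP precedence follows text about endpoints and analyses. This stands. A reader might infer that sites will handle the same patient differently, but the documents do not support that, since there is one operative text for sites.

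Second, the graver outcomes are not left unmanaged: 7.9 has rules for plan with intent and for behaviour, plus a general duty to observe. This also stands, and it is why the gap narrows to ideation without intent.

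Third, the SAP's wider meaning takes in every protocol-positive patient, so the listing loses no one. That is correct.

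Fourth, a listing can be tallied by arm once treatment is known, neither document plans a formal safety test, and the entry criteria make few events likely. A reader might infer that the endpoint cannot be set against placebo at all. That goes too far, because a tally is possible. But no tally is prespecified, a listing carries no percentages, and protocol 9.7 promises them.

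Fifth, the Appendix J problem could be called editorial, because discontinuation rules exist in 7.9. In part it is. Still, a stated rule points to criteria that are not where it says they are, and the reader is not sent to 7.9 instead.

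**Conclusion.** The point holds in three limited parts. The term for a positive finding differs between protocol 7.9 and SAP 8.6, with ideation without intent as the outcome whose formal evaluation is unclear. Protocol 3.4 and 4.3 refer to discontinuation criteria that Appendix J does not contain. SAP 8.6 specifies less output than protocol 9.7 requires for a named safety endpoint.

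Its size is modest. It touches no efficacy inference, error rate or power. The number of patients affected cannot be worked out, because neither document gives a rate of ideation by category, and I put no figure on it. It is more than missing detail, since a stated rule leads nowhere and the SAP falls short of the protocol's own commitment. The conclusion assumes that the supplied text of Appendix J and SAP 8.6 is complete; neither shows a redaction.

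**What to change.** 1. Reconcile the meaning of a positive eC-SSRS finding across protocol 7.9, 3.4 and 4.3 and SAP 8.6, and state whether ideation without intent calls for the formal evaluation. Which clinical rule applies is for those responsible for the protocol; this review does not choose one.
2. Correct the reference in protocol 3.4 and 4.3, so that it leads to wherever the suicidality discontinuation criteria are set out.
3. Add to SAP 8.6 a descriptive table by treatment group: counts and percentages of patients with each ideation category and with behaviour, at baseline and postbaseline. Keep the listing. No test is needed.
4. Say which assessment is baseline for this table. Visit 1 uses the Baseline/Screening form and visit 2 the Since Last Visit form, so the general rule in SAP 4.2 (last value before the first dose) would pick the visit 2 form, which looks back only to the previous visit.

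The cost is one protocol clarification and one SAP table. The eC-SSRS is already completed at all five scheduled visits, so there is no new data collection and no added burden on patients.

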7.10. Concomitant Therapy or Medication

Concomitant therapy or medication use will be monitored throughout the study. Details of prohibited medications are found in Section 5.6.

7.11. Injection Site Assessments

Injection site assessments will be performed immediately (+10 minutes) and 1 hour (±15 minutes) after receiving each dose of the IMP. The injection site(s) will be assessed for erythema, induration, and ecchymosis.

Severity will be graded according to the following criteria:

- Injection site erythema, induration, and ecchymosis will be graded according to measurements: absent, 5 to ≤50 mm (mild), >50 to ≤100 mm (moderate), and >100 mm (severe). Induration must be assessed by careful superficial palpation avoiding pressuring or squeezing the injection site.
- For spontaneous report of local pain after the injection, it will be measured as summarized in Table 5.

Table 5: Severity of Pain Scale for Injection Site Assessments

Symptom	Severity grade	Assessment
Pain	0	Absent
	1	Mild
	2	Moderate
	3	Severe

If a patient has severe injection site induration, erythema, ecchymosis, has severe injection site induration, erythema, ecchymosis, or pain at 1 hour after completion of IMP administration, the

patient will be reassessed at 3 hours (± 15 minutes) after completion of IMP administration and hourly (± 15 minutes) thereafter until the reaction is of moderate or less severity.

Appropriate treatment may be provided if necessary, in which case it must be recorded as concomitant medication.

Injection-site reactions (injection site erythema, induration, ecchymosis, and pain) should be recorded as adverse events.

8. ASSESSMENT OF PHARMACOKINETICS/BIOMARKERS/ PHARMACOGENOMICS/IMMUNOGENICITY/ANCILLARY STUDIES

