1.3.1. Known and Potential Benefits and Risks of the Test Investigational Medicinal Product(s)

Results from Phase 2b clinical studies have demonstrated statistically significant reductions in mean headache hours after 1, 2, and 3 months of sc fremanezumab treatment in patients with chronic migraine and statistically significant reductions in monthly migraine days after 1, 2, and 3 months of fremanezumab treatment in patients with episodic migraine. Results for several secondary/exploratory endpoints also showed fremanezumab to be superior to placebo.

Fremanezumab has generally been well tolerated over the ranges of doses evaluated (single iv infusions at 0.02 to 2000 mg in healthy subjects, multiple iv infusions at 30 to 300 mg in healthy subjects, and multiple sc doses at 225 to 900 mg in healthy subjects and migraine patients). The most common treatment-emergent adverse events across all patients/subjects studied were mild to moderate transient general administration site disorders/reactions. Other commonly reported treatment-emergent adverse events were headache, back pain, and upper respiratory tract infection.

Reports of mild to moderate transient administration site disorders/reactions, including injection site bruising, injection site swelling, administration site pain, injection site pain, injection site pruritus, injection site dermatitis, injection site rash, injection site edema, injection site discomfort, injection site hemorrhage, injection site irritation, injection site mass, and injection site hematoma, have occurred with sc administration. In addition, reports of mild and transient infusion site pain and swelling following iv administration have occurred. Among these events, the following have been identified as adverse drug reactions (identified risks): injection site erythema, administration site pain, injection site pain, injection site pruritus, and injection site dermatitis. None of these identified risks are considered important risks.

Infusion-related reaction and drug hypersensitivity were also identified as adverse drug reactions. To date, 1 subject who received fremanezumab iv had a non-serious infusion-related reaction, and 1 patient who received fremanezumab via the sc route had a non-serious event of drug hypersensitivity. Both events resolved following IMP discontinuation and treatment with diphenhydramine and methylprednisolone. Neither of these identified risks are considered important risks.

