- ^u Responses at week 1 will be recorded in the electronic diary device at home, and responses at all other time points will be entered into the investigational site tablet.
- ^v Patients will return the wearable sensor if they do not rollover into the long-term safety study (Study TV-48125-CNS-30058) or if they rollover into the long-term safety study but do not wish to continue participating in the wearable sensor substudy.
- ^w The eC-SSRS Baseline/Screening version will be completed at visit 1, and the eC-SSRS Since Last Visit version will be completed at all other visits, including unscheduled visits. Results from both versions will be entered into the investigational site tablet.
- ^x Patients randomized to the 900-mg iv loading dose group will receive 900 mg of fremanezumab administered via an approximately 1-hour iv infusion followed by placebo as 3 sc injections at visit 2 (week 0) and fremanezumab at 225 mg administered as single sc injections (225 mg/1.5 mL) at visits 3 and 4 (weeks 4 and 8, respectively). Patients randomized to the fremanezumab 675-mg sc quarterly group will receive placebo administered via an approximately 1-hour iv infusion followed by fremanezumab at 675 mg administered as 3 sc injections (225 mg/1.5 mL) at visit 2 (week 0) and placebo administered as single sc injections at visits 3 and 4 (weeks 4 and 8, respectively). Patients in the placebo group will receive placebo administered via an approximately 1-hour iv

Clinical Study Protocol with Amendment 02

infusion followed by placebo administered as 3 sc injections at visit 2 (week 0) and placebo administered as single sc injections at visits 3 and 4 (weeks 4 and 8, respectively).

^y Patients will be assessed for hypersensitivity reactions and anaphylaxis during and after administration of the IMP (through 1 hour postdose).

^z Injection site will be assessed for erythema, induration, ecchymosis, and pain immediately (+10 minutes) and 1 hour (± 15 minutes) after IMP administration. If a patient has severe injection site induration, erythema, ecchymosis, or pain at 1 hour after completion of IMP administration, the patient will be reassessed 3 hours (± 15 minutes) after completion of IMP administration and hourly (± 15 minutes) thereafter until the reaction is of moderate or less severity.

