7.1.3. Severity of an Adverse Event

The severity of each adverse event must be recorded as 1 of the following:

- Mild:** No limitation of usual activities
- Moderate:** Some limitation of usual activities
- Severe:** Inability to carry out usual activities

For severity grading of local tolerability (injection site erythema, induration, ecchymosis, and pain), refer to Section 7.11.

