8.3. Adverse Events

Adverse events will be recorded from time informed consent is obtained through the end of study participation.

The following are considered protocol-defined adverse events of special interest to be sent to the sponsor's Global Patient Safety and Pharmacovigilance Department for evaluation: ophthalmic-related adverse events of at least moderate severity, events of possible drug-induced liver injury (aspartate aminotransferase or alanine aminotransferase $\geq 3 \times$ the upper limit of normal [ULN], total bilirubin $\geq 2 \times$ the ULN, or international normalized ratio >1.5), Hy's Law events, or events of anaphylaxis and severe hypersensitivity reactions.

All adverse events will be coded using MedDRA (version 18.1). Each patient will be counted only once in each preferred term or SOC category for the analyses of safety. Summaries will be presented for all adverse events (overall and by severity), adverse events determined by the investigator to be related to test IMP (defined as related or with missing relationship) (overall and by severity), serious adverse events, and adverse events causing withdrawal from the study. Adverse events with the missing flag indicating serious will be excluded from the summary of serious adverse events but included in the summary of non-serious adverse events.

Summaries for injection site and infusion-related adverse events and protocol-defined adverse events of special interest will be presented (overall and by severity).

Listings for deaths, serious adverse events, adverse events leading to discontinuation, injection site and infusion-related adverse events, and protocol-defined adverse events of special interest will be presented. In addition, listings for MedDRA dictionary terms for adverse event descriptions and adverse event preferred terms by patient number and treatment group will be presented.

Spontaneous abortion or an elective abortion due to developmental anomalies will be reported as a serious adverse event (protocol Section 7.2). These serious adverse events will be listed separately if applicable.

Summaries will include treatment-emergent adverse events which are defined as adverse events occurring at or after the first dose of the IMP. The listing will include all adverse events recorded.

Adverse events for patients who did not meet screening criteria will be listed.

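### Infusion-site reactions fall outside the structured local checks and are graded on a different scale, so they are detected less sensitively and cannot be compared with injection-site reactions

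*Protocol*

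**What the plan says.** Section 7.11 sets the timing: "Injection site assessments will be performed immediately (+10 minutes) and 1 hour (±15 minutes) after receiving each dose of the IMP". It names the object of the check as the injection site: "The injection site(s) will be assessed for erythema, induration, and ecchymosis". Those three signs are graded by size, "absent, 5 to ≤50 mm (mild), >50 to ≤100 mm (moderate), and >100 mm (severe"), and pain is graded from absent to severe in Table 5. Table 2 footnote z, Appendix B at visit 2 and SAP 8.4 likewise refer to injection sites. None of them names the infusion site.

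The link from adverse-event severity to this scale is equally narrow. Section 7.1.3 says: "For severity grading of local tolerability (injection site erythema, induration, ecchymosis, and pain), refer to Section 7.11". Any other event is mild, moderate or severe according to how far it limits what the patient usually does.

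Infusion-site reactions are a known finding. Section 1.3.1 states that "reports of mild and transient infusion site pain and swelling following iv administration have occurred". The SAP reports both kinds of event in Section 8.3: "Summaries for injection site and infusion-related adverse events and protocol-defined adverse events of special interest will be presented (overall and by severity"). SAP 8.1 has safety summarised descriptively by treatment group.

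Two current passages disagree about pain at the sc sites. Section 7.11 grades it "For spontaneous report of local pain after the injection", whereas footnote z schedules it: "Injection site will be assessed for erythema, induration, ecchymosis, and pain immediately (+10 minutes) and 1 hour".

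**The concern.** At week 0 the two active arms receive drug through different routes, and only one of those routes is examined on a schedule. In the 675-mg arm, staff look at and measure the sites that received active drug. In the 900-mg arm, the same examination is spent on three placebo sites, and the vein that received the active infusion is not on the list.

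Two things are at stake. First, an open question and general observation are likely to find fewer mild, short-lived skin signs than a directed look at the site, so the trial is less able to describe a reaction it already expects. Second, the words mild, moderate and severe mean different things at the two kinds of site, yet both feed summaries by severity. A reader who sets the two active columns side by side would be comparing different methods of ascertainment and different grades.

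**Working it through.** The plan states no figure for local reactions, so there is none to reproduce. The check is to trace which sites are examined, how the rest are found, and how each is graded.

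**1. Which sites are checked** (treatments from Section 5.1.1.1 and 5.1.2; checks from Section 7.11, footnote z and Appendix B)

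| Visit | Site | 900-mg arm | 675-mg arm | Placebo arm | Scheduled local check |
|---|---|---|---|---|---|
| Week 0 | Infusion | active 900 mg | placebo | placebo | no |
| Week 0 | 3 sc injections | placebo | active 675 mg | placebo | yes |
| Weeks 4 and 8 | 1 sc injection each | active 225 mg | placebo | placebo | yes |

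Each arm has 3 + 1 + 1 = 5 checked injections and one unchecked infusion. Share of planned active drug whose entry site is checked:

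- 900-mg arm: (225 + 225) / (900 + 225 + 225) = 450/1350 = 33%. Unchecked: 900/1350 = 67%.
- 675-mg arm: 675/675 = 100%.

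These shares describe coverage. They do not measure bias.

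**2. How infusion-site reactions are found instead**

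Section 7.1.2 requires staff to ask about adverse events at every contact and to record signs that they observe as well as those reported. Appendix B schedules a further inquiry after dosing at visit 2, before the patient goes home. This is active questioning, but not a directed examination of the site.

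**3. How the two scales treat the same lesion**

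| Lesion | At an injection site (7.11) | At an infusion site (7.1.3) |
|---|---|---|
| 60-mm erythema, no activity limited | moderate | mild |
| 30-mm erythema, some activity limited | mild | moderate |

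The scales disagree in both directions, so the grades are not interchangeable, and neither scale is uniformly more lenient.

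**4. Illustration of size (all inputs assumed; the documents give no rates)**

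Let p be the true reaction rate at the active week-0 site, b the rate at the iv arm's placebo injection sites, and c the share of infusion-site reactions found without a structured check. Take structured checks to find everything, and the two kinds of reaction to be independent.

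- True iv-arm rate of any local reaction at week 0: 1 − (1 − p)(1 − b)
- Recorded rate: 1 − (1 − pc)(1 − b)
- Shift, recorded minus true: −p(1 − c)(1 − b)

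With p from 10% to 30% and b from 0% to 20%:

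| c | Smallest shift (p = 10%, b = 20%) | Largest shift (p = 30%, b = 0%) |
|---|---|---|
| 0.3 | −0.10 × 0.7 × 0.8 = −5.6 points | −0.30 × 0.7 × 1 = −21.0 points |
| 0.6 | −0.10 × 0.4 × 0.8 = −3.2 points | −0.30 × 0.4 × 1 = −12.0 points |
| 0.9 | −0.10 × 0.1 × 0.8 = −0.8 points | −0.30 × 0.1 × 1 = −3.0 points |

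The shift is downward by construction, and its size runs from negligible to large depending on inputs that nobody can read from the plan. It covers week 0 only. At weeks 4 and 8 the iv arm has active injections under structured checks while the 675-mg arm has placebo, so the whole-study picture does not follow from it.

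**The case against.** The case for leaving the plan alone is substantial.

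- **Patients are asked and watched.** Besides the questioning in step 2, footnote y has them observed for hypersensitivity through 1 hour after dosing, Section 5.5.1 keeps them on site for at least 60 minutes after the infusion, and a blood sample is drawn when the infusion ends. A reader might infer that infusion-site reactions are recorded only if the patient volunteers them. The documents do not support that.
- **No comparison of the routes is planned.** Safety is descriptive and tolerability is left undefined (SAP Section 9). Section 5.3.1 speaks of confirming the benefit of each loading form, in the context of a rapid response, not of local harm.
- **The double dummy protects the planned contrasts.** Every arm gets one infusion and five injections, collected in the same way. Infusion sites and injection sites can each be compared, active against placebo, without differential collection.
- **The gap is narrower for pain and swelling.** Under Section 7.11 even sc pain rests on spontaneous report. Swelling, one of the two infusion-site reactions named in Section 1.3.1, is not a listed sign in 7.11.
- **The events are not lost from reporting.** SAP 8.3 summarises and lists infusion-related events. Section 7.1.2 also defers details to a Safety Monitoring Plan that is not among the documents.

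All of this limits the point, but none of it supplies an infusion-site check or a common scale. Questioning and general presence are not an examination of the site. Identical collection across arms prevents differential collection against placebo, but it does not restore missed events. A descriptive table still invites readers to compare columns, and nothing in SAP 8.3 warns them that the grades differ.

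**Conclusion.** The point holds as a minor weakness in safety ascertainment. In the readable text, infusion-site reactions have no structured check and are graded by activity limitation instead of the 7.11 sizes or Table 5. For the 900-mg arm this applies to the entry site of 67% of its active drug. The consequences are lower sensitivity for a known reaction, and rates and grades that should not be set against those for injection sites.

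A reader might go further and conclude that the by-arm safety tables favour the iv regimen whatever the truth. The documents do not support that. Each active-versus-placebo contrast is collected identically, no iv-versus-sc test is planned, the two severity scales cross in both directions, and the iv arm's active injections at weeks 4 and 8 are checked. The illustrative shift of −0.8 to −21.0 points at week 0 depends wholly on assumed rates. Neither a size nor a net whole-study direction can be fixed from the plan. Efficacy is untouched.

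The conclusion assumes that the Safety Monitoring Plan does not already add an infusion-site check.

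**What to change.** **If conduct can still change:**

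- In Section 7.11, Table 2 footnote z and Appendix B (visit 2), extend the two existing checks to the infusion site in all three arms, with the same grades for erythema, induration, ecchymosis and pain. State where swelling is to be recorded.
- Extend the cross-reference in Section 7.1.3 to infusion-site reactions, so that one scale serves both kinds of site.
- In SAP 8.3 and 8.4, tabulate infusion-site and injection-site reactions separately.

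**If it cannot:** still tabulate them separately, add a note that ascertainment and grading differ, and make no direct comparison between the two.

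**In either case:** reconcile Section 7.11 with footnote z on whether sc-site pain is assessed on schedule or graded only when reported.

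**Cost:** one more line on the visit 2 assessment form and some wording. The same staff see the patient at the same times, so no visit or procedure is added. The downside is that more mild infusion-site events will be recorded in every arm.
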